#### 4.2.2. Additional Inclusion Criteria for Sub-Study Patients Only

1. Willing to discontinue glucosamine sulfate and chondroitin sulfate treatments during the initial 16 weeks of treatment
2. Stable treatment with glucosamine sulfate and chondroitin sulfate treatments must be stopped during the pre-randomization period.
3. Provide consent to allow all radiographs/other imaging and medical/surgical/hospitalization records for care received elsewhere during the study period to be shared with investigator

#### 4.2.3. Exclusion Criteria

A patient who meets any of the following criteria will be excluded from the study:

1. History or presence at the screening visit of non-OA inflammatory joint disease (eg, rheumatoid arthritis, lupus erythematosus, psoriatic arthritis, pseudogout, gout, spondyloarthropathy, polymyalgia rheumatica, joint infections within the past 5 years), Paget's disease of the spine, pelvis or femur, neuropathic disorders, multiple sclerosis, fibromyalgia, tumors or infections of the spinal cord, or renal osteodystrophy
2. History or presence on imaging of arthropathy (osteonecrosis, subchondral insufficiency fracture, rapidly progressive osteoarthritis type 1 or type 2), stress fracture, recent stress fracture, neuropathic joint arthropathy, hip dislocation (prosthetic hip dislocation is eligible), knee dislocation (patella dislocation is eligible), congenital hip dysplasia with degenerative joint disease, extensive subchondral cysts, evidence of bone fragmentation or collapse, or primary metastatic tumor with the exception of chondromas or pathologic fractures during the screening period
3. Signs or symptoms of carpal tunnel syndrome within 6 months of screening

4. Patient is not a candidate for MRI
5. Is scheduled for a joint replacement surgery to be performed during the study period
6. Systemic (ie, oral or intramuscular) corticosteroids within 30 days prior to the screening visit. Intra-articular corticosteroids in the index joint within 12 weeks prior to the screening visit, or to any other joint within 30 days prior to the screening visit (topical, intra-nasal, and inhaled corticosteroids are permitted)
7. History or presence at the screening visit of autonomic neuropathy, diabetic neuropathy, or other peripheral neuropathy, including reflex sympathetic dystrophy
8. History or diagnosis of chronic autonomic failure syndrome including pure autonomic failure, multiple system atrophy (Shy-Drager syndrome)
9. Poorly controlled diabetes (defined as any single value of hemoglobin A1c [HbA1c] >9.0%) at the screening visit
10. Known history of human immunodeficiency virus infection
11. Known history of ocular herpes simplex virus, herpes simplex virus pneumonia, or herpes simplex virus encephalitis
12. History of sickle cell disease, including S-C disease and S- $\beta$  thalassemia
13. Confirmed elevated screening alanine aminotransaminase (ALT) or aspartate aminotransaminase (AST)  $\geq 2.5$  times the ULN
14. Resting heart rate of <50 beats per minute (bpm) or >100 bpm (by vital sign assessment or as captured during ECG assessment) at the screening or randomization visits
15. History or presence of 2nd or 3rd degree heart block, 1st degree heart block with abnormal QRS, or bifascicular block by ECG assessment at the screening visit
16. History or presence of orthostatic hypotension, as defined in Section 6.3.4.6, at the screening or randomization visits
17. History of poorly controlled hypertension
  - Systolic blood pressure  $\geq 180$  mm Hg or diastolic blood pressure  $\geq 110$  mm Hg at the screening visit
  - Systolic blood pressure of 160 mm Hg to 179 mm Hg or diastolic blood pressure of 100 mm Hg to 109 mm Hg at the screening visit, AND a history of end-organ damage (including history of left ventricular hypertrophy, heart failure, angina, myocardial infarction, stroke, transient ischemic attack [TIA], peripheral arterial disease and moderate to advanced retinopathy [hemorrhages or exudates, papilledema])
18. Congestive heart failure with NY Heart Classification of stage III or IV
19. Transient ischemic attack (TIA) or cerebrovascular accident within the past 12 months prior to the screening visit, or myocardial infarction, or acute coronary syndromes within the past 6 months prior to the screening visit

20. Significant concomitant illness including, but not limited to, psychiatric, cardiac, renal, hepatic, neurological, endocrinological, metabolic, or lymphatic disease that, in the opinion of the investigator, would adversely affect the patient's participation in the study
  21. New major illness diagnosed within 2 months prior to the screening visit
  22. Known history of infection with hepatitis B virus. Patients with a history of hepatitis B are eligible if there is documentation of a negative test for hepatitis B surface antigen and a positive test for antibodies to the hepatitis B virus surface antigen.
  23. Known history of infection with hepatitis C virus. Patients with a history of hepatitis C are eligible if there is documentation of a negative hepatitis C virus RNA test.
  24. History or presence of malignancy within the last 5 years prior to screening, except patients who have been treated successfully with no recurrence for >1 year of basal cell or squamous cell carcinoma of the skin or in-situ cervical cancer
  25. Known allergy or sensitivity to doxycycline or related compounds, or monoclonal antibodies
  26. History of (within 5 years prior to the screening visit) current alcoholism, alcohol abuse, substance abuse, or abuse of prescription pain medication
  27. History of cannabis use for the treatment of pain within the past 6 months prior to the screening visit
  28. Ongoing participation in a clinical research study evaluating another investigational drug or having received another investigational product with 30 days or 5 half-lives of the screening visit, whichever is longer
  29. Exposure to an anti-NGF antibody prior to the screening visit or known sensitivity or intolerance to anti-NGF antibodies, or participation in a clinical trial evaluating anti-NGF antibodies
  30. Member of the clinical site study team and/or his/her immediate family
  31. Pregnant or breast-feeding women
  32. Women of childbearing potential who have a positive pregnancy test result or do not have their pregnancy test result at baseline
  33. Women of childbearing potential\* who are unwilling to practice highly effective contraception prior to start of the first treatment, during the study, and for at least 20 weeks after the last dose. Highly effective contraceptive measures include stable use of combined (estrogen and progestogen containing) hormonal contraception (oral, intravaginal, transdermal) or progestogen-only hormonal contraception (oral, injectable, implantable) associated with inhibition of ovulation initiated 2 or more menstrual cycles prior to screening; intrauterine device; intrauterine hormone-releasing system; bilateral tubal ligation; vasectomized partner; and or sexual abstinence†, ‡
- \* Postmenopausal women must be amenorrheic for at least 12 months in order not to be considered of childbearing potential. Pregnancy testing and contraception are not required for women with documented hysterectomy or tubal ligation.

† Sexual abstinence is considered a highly effective method only if defined as refraining from heterosexual intercourse during the entire period of risk associated with the study treatments. The reliability of sexual abstinence needs to be evaluated in relation to the duration of the clinical trial and the preferred and usual lifestyle of the subject.

‡ Periodic abstinence (calendar, symptothermal, post-ovulation methods), withdrawal (coitus interruptus), spermicides only, and lactational amenorrhoea method (LAM) are not acceptable methods of contraception. Female condom and male condom should not be used together.

Note: HIV and/or hepatitis testing will be performed on a country-by-country basis, according to local guidelines if required by regulatory authorities or ethics boards.

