### 3. STUDY DESIGN

#### 3.1. Study Description and Duration

This study will further characterize the safety profile of fasinumab including the incidence of AEs and provide data on long-term exposure. A subset of approximately 1000 patients will also participate in a sub-study to characterize the efficacy of fasinumab. Participation in the sub-study will last for the first 16 weeks of this study; patients will then be rolled over into the long-term safety study.

The study consists of a screening period of up to 30 days (Screening Period), a 7 to 10 day pre-randomization period (Pre-Randomization Period), a 16-week randomized, double-blind, placebo-controlled treatment period (Treatment Period 1), a 36-week, double-blind, placebo-controlled treatment period (Treatment Period 2) in which non-NSAID standard-of-care pain medications can also be used in the event of inadequate pain relief for OA pain, a 24-week follow-up period with in-clinic visits (Follow-up Period), and an end of study phone contact at 52 weeks following the last dose of study drug to evaluate the number of patients who have undergone JR surgery, are scheduled for JR surgery, or on a waiting list for JR surgery (Figure 1).

- **Screening Period (up to 30 days before the pre-randomization period):** After informed consent has been signed, eligibility for enrollment will be determined based upon parameters assessed during the screening and pre-randomization periods. X-rays of the shoulders, hips and knees will be performed during the screening period. Magnetic resonance imaging (MRI) of the index and contralateral joint must be performed and assessed by the central reader. Any knee or hip joint with a K-L score of  $\geq 3$  will have an MRI completed during the screening period. Pre-randomization visits cannot occur until the MRIs of those joints have been completed and the central reader confirms that there are no exclusionary findings. During the screening period, all patients may continue to take their current treatment regimen for OA pain.

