- **Follow-up Period (for 24 weeks after the last dose of study drug, up to week 72):** Patients will be followed for an additional 24 weeks following administration of the last dose of study drug. Patients who were discontinued from 3 mg Q4W or 6 mg Q8W fasinumab under amendment 7 were immediately entered into the follow-up period. Patients will have safety assessments performed at clinic visits, which will occur at 4 weeks, 12 weeks, and 24 weeks after the last dose of study drug. Additionally, a phone contact will be conducted at 8 weeks following the last dose of study drug to monitor for AEs and concomitant medications.

[figure not shown]
During the follow-up period, patients must still only use the limited use amounts of NSAIDs for non-OA pain or fever. Patients may increase their dose of NSAIDs beyond the limit outlined for treatment period 2 starting 16 weeks after their last dose of study drug.

All AEs will continue to be monitored during this period.

If a patient must undergo JR surgery during the treatment or follow-up periods (up to week 24 after the last dose), then the patient will be asked to complete post-surgery follow-up assessments, as outlined in [Table 5](#).

- **End of Study Phone Contact (week 100):** A phone contact questionnaire will be conducted at 52 weeks following the last dose of study drug to document patient status with regard to JR surgery (if a patient underwent JR, is scheduled to have JR surgery, or is on a waiting list for JR surgery). Patients who had an AA will have an MRI performed of the affected joint(s). If the affected joint has undergone JR an X-ray may be substituted for an MRI.

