#### 7.6.1.4. Joint Replacement Surgery

An end of study phone contact will be conducted at 52 weeks following the last dose of study drug to evaluate the number of patients who have undergone or are scheduled for JR surgery as described in Section 6.3.4.9. Any elective JR surgery planned before completion of the ICF would be part of the exclusion criteria and would not be considered an AE.

After signing of the ICF, report JR surgery as an AESI if the JR surgery is an elective event that is not associated with a new/worsening AE.

Do not report JR surgery as an AE/AESI if the JR surgery is for the treatment of a new or worsening AE. In this case, the new or worsening AE should be the reported AE/AESI term.

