4.5.1. Primary Safety Variables

The primary safety endpoint in the study is safety monitoring including AE incidence, SAE, incidence, AESI incidence, changes in safety lab analyses, and incidence of anti-fasimumab antibody formation from baseline to week 52 (treatment period 1 and 2) and to week 72 (end of follow-up period).

More specifically, this includes:

- Incidence of adjudicated arthropathy events
- Incidence of destructive arthropathy events
- Incidence of JR (All JRs and AESI JRs) events – including endpoint for all JRs by the telephone survey approximately 52 weeks after the last dose of study drug
- Incidence of peripheral neurosensory AESI events

- Incidence of sympathetic nervous system dysfunction AESI events
- AE incidence, SAE incidence, changes from baseline in safety laboratory analyses, and incidence of anti-fasimumab antibody formation
- Change from baseline in minimum joint space width of the index joint (knee, hip)
- Incidence of confirmed orthostatic hypotension from baseline

The raw incidence rate is defined as the number of events divided by the duration of the observation period and presented as number of events per 100 patient-years.

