4.5.10. Other Safety Variables

- Joint Pain Questionnaire:
 - Number of subjects with significantly worse joint pain in any joint at each scheduled visit
 - Number of subjects with significantly worse joint pain by joint at each scheduled visit
- Joint space width for the index joints as well as other knee or hip joints at each scheduled visit
- Joint replacement:
 - number and percentage of patients with joint replacement (all JRs)
 - time to joint replacement decision (all JRs)

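### Exclusion criterion 5 covers only scheduled joint replacement, which is narrower than the exclusion Section 7.6.1.4 says is in place, and the SAP has no rule for replacements decided before first dose

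*Protocol*

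**What the plan says.** - **Eligibility.** Protocol 4.2.3, criterion 5, excludes a patient who "Is scheduled for a joint replacement surgery to be performed during the study period". Inclusion criterion 12 (4.2.1) requires willingness to consider total JR.
- **What the safety section says about eligibility.** Protocol 7.6.1.4: "Any elective JR surgery planned before completion of the ICF would be part of the exclusion criteria and would not be considered an AE". It goes on to say that, after consent is signed, sites should "report JR surgery as an AESI if the JR surgery is an elective event" not associated with a new or worsening AE.
- **Follow-up.** The end-of-study call (Protocol 3.1) records whether the patient has had JR, "is scheduled to have JR surgery, or is on a waiting list for JR surgery".
- **Analysis.** SAP 4.5.1 lists "Incidence of JR (All JRs and AESI JRs) events" among the primary safety variables, including an "endpoint for all JRs by the telephone survey approximately 52 weeks after the last dose of study drug". SAP 4.5.10 adds the number and percentage of patients with any JR. Time to JR decision is exploratory (Protocol 8.3, SAP 4.5.2).
- **Effect measures.** SAP 5.1.7.1 reports incidence rate ratios and rate differences, each with a 95% confidence interval. SAP 5.1.8 uses Kaplan-Meier and Cox regression for time-to-event endpoints.

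**The concern.** Section 7.6.1.4 relies on an exclusion that the eligibility list does not contain. *Planned* is wider than *scheduled*, and sites screen against Section 4.2.3, not against a sentence in the section on monitoring adverse events of special interest (AESIs). A patient who has agreed to surgery and is waiting for a date can pass criterion 5 and satisfies inclusion 12. Participation lasts up to 105 weeks (Synopsis), so the operation may well fall within the trial. The surgery would then count among all JRs, although 7.6.1.4 says it is not an AE.

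This matters because JR is a primary safety variable, and time to total joint replacement was among the imbalances behind the data monitoring committee's recommendation to stop two regimens (Protocol 1.1 and 1.3.2). Replacements decided before the first dose add background events to every arm. They also leave time to JR decision without a usable event time.

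**Working it through.** No sample size, power or alpha figure in the plan depends on this point, so there is no stated figure to reproduce. The check has two parts.

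**1. The text, followed through for one patient.** Take a patient wait-listed for JR, without a date, before consent.

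| Provision | What it does with this patient |
|---|---|
| Protocol 4.2.3, criterion 5 | Not clearly excluded: no surgery is scheduled, and none can be placed within the study period |
| Protocol 4.2.1, criterion 12 | Met |
| Protocol 7.6.1.4, pre-consent sentence | Said to be excluded; surgery is not an AE |
| Protocol 7.6.1.4, post-consent sentence | Can be read as making the surgery an AESI, since it is elective and performed after consent |
| SAP 4.5.3 | Cites 7.6.1.4 but describes AESI JR as elective and not due to new or worsening disease; the pre-consent clause is not repeated |
| SAP 4.5.1 and 4.5.10 | Surgery counts among all JRs; no carve-out |
| SAP 4.5.2 and 5.1.8 | *JR decision* is not defined; no rule for a decision dated before Day 1 |

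There is a second window. The pre-consent clause stops at the consent form, but dosing starts later: screening lasts up to 30 days from consent (6.2.1) and the pre-randomisation period is 7 to 10 days (6.2.3). A JR decided in those 30 + 10 = 40 days at most, and not yet scheduled, is outside both the clause and criterion 5. After consent it is reportable as an AESI if elective.

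**2. Effect on the estimates (illustrative).** The documents give neither a JR risk nor a wait-list prevalence, so every input here is assumed. Let p0 be the placebo risk of a newly decided JR, RR the true risk ratio, and w the share of each arm that enters with JR already decided and then has it. With equal observation time per arm:

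- observed ratio = (RR × p0 + w) / (p0 + w)
- observed difference = (RR × p0 + w) − (p0 + w) = p0 × (RR − 1), which does not depend on w

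With p0 = 3.0% and 4.5% on fasinumab (RR = 1.50):

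- w = 0.5%: 5.0/3.5 = 1.43
- w = 1%: 5.5/4.0 = 1.38
- w = 2%: 6.5/5.0 = 1.30
- the difference stays at 1.5 percentage points throughout

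Over a wider range:

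| p0 | True ratio | w = 0.5% | w = 1% | w = 2% |
|---|---|---|---|---|
| 2% | 1.5 | 1.40 | 1.33 | 1.25 |
| 2% | 2.0 | 1.80 | 1.67 | 1.50 |
| 4% | 1.5 | 1.44 | 1.40 | 1.33 |
| 4% | 2.0 | 1.89 | 1.80 | 1.67 |

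The hazard ratio is diluted in the same direction wherever these cases are counted as events. Whether they are counted depends on how the decision is dated, which the SAP leaves open.

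**The case against.** **Scheduled may be meant to include wait-listed.** The Synopsis (Study Design), 6.2.9, 6.3.4.9 and the Table 4 footnote put the waiting list in brackets after *scheduled*. Section 7.6.1.4 describes the call as covering JR undergone or scheduled, and refers to 6.3.4.9, where the waiting list is named. Against that, the Synopsis (Procedures) and Protocol 3.1 list three separate states; 3.1 gives the purpose of the call as "to evaluate the number of patients who have undergone JR surgery, are scheduled for JR surgery, or on a waiting list for JR surgery". The wording is therefore ambiguous. That is itself a reason to align it, and it does not close the gap between *scheduled* and *planned*.

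**A reader might infer that waiting-list status is itself counted as a JR event.** The documents do not support that. The call collects the status, but SAP 4.5.1, 4.5.10 and 7 speak of JRs, and none says that being scheduled or wait-listed is an event. The point concerns surgery that is actually performed.

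**A reader might infer that the gap makes the drug look safer overall.** Only the ratio measures move. The rate difference, which SAP 5.1.7.1 also reports, does not change under the model above, and randomisation balances these cases in expectation.

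**The model is simple.** It assumes that every pre-decided patient has the surgery, equally in each arm. Only the decision predates dosing; pain relief or joint damage on treatment could still change whether or when surgery happens. This stands. It is also why these JRs should not be dropped from the main analysis.

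**Conclusion.** The concern holds as an inconsistency between eligibility, safety reporting and analysis. Section 7.6.1.4 describes an exclusion for planned JR that no listed criterion delivers. A patient wait-listed or committed without a date can be enrolled under the list as written, and the surgery would then count among all JRs, although 7.6.1.4 says it is not an AE. The SAP also has no rule for a JR decision made before first dose.

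The statistical consequence is dilution of the rate ratio and hazard ratio towards 1, with the rate difference about unchanged. It is not a false excess on fasinumab. Its size cannot be stated from the documents. The ratios above rest on assumed risks and on an assumed 0.5% to 2% share; if few such patients were enrolled, the effect is negligible. The point is worth acting on because JR is a primary safety variable and the correction is cheap.

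**What to change.** 1. **Protocol 4.2.3.** For remaining enrolment under amendments 8 and 9, reconcile criterion 5 with 7.6.1.4 so that it covers JR that is scheduled, wait-listed or otherwise planned at the time of consent. Cost: one line in an amendment and one screening question. A few patients become ineligible. If enrolment is complete, only the SAP changes below apply.
2. **SAP 4.5.1, 4.5.2, 4.5.10 and 5.1.8.**
   - Keep all JRs as the main analysis.
   - Define *JR decision* and how it is dated.
   - State whether scheduled or wait-listed status at the call counts as an event.
   - Flag JRs decided before first dose, which also covers the interval between consent and dosing.
   - Add a sensitivity analysis of the JR rate and of time to JR decision without the flagged JRs, saying whether those patients stay in the risk set.

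The SAP changes cost a few sentences and one extra table, plus a decision date. The schedules of events show no such item at screening. For patients who have had surgery, the JR-related medical history required by Protocol 6.3.4.10 and Table 5 is a possible source. The flag should be assigned blind to treatment.

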#### 4.2.4. Additional Exclusion Criteria for Sub-Study Patients Only

1. Four or more consecutive missed diary entries during the pre-randomization period
2. Trauma to the index joint within 3 months prior to the screening visit
3. Use of a monoamine reuptake inhibitor, tricyclic antidepressants, selective serotonin reuptake inhibitors and serotonin norepinephrine reuptake inhibitors for treatment of pain within 4 weeks prior to the screening visit
4. Presence of orthostatic hypotension at the pre-randomization visit
5. Has positive urine drug test results during screening (eg, amphetamines/methamphetamines, barbiturates, benzodiazepines, cannabinoids, cocaine, and opiates), unless in the opinion of the investigator, the positive test results may be due to the patient's current permitted medications.
6. History of hospital admission for depression or suicide attempt within 5 years or active, severe major depression at screening

